6.1.9 Duration of Therapy

2 sessions of PLIFUS/sham administration (delivered over a total of 10 minutes). An evaluable participant will be defined as having completed all sonication/sham sessions.

6.1.10 Tracking of Dose

A "Subject Dose Log" form will record the FUS exposure for each subject. This will include date and time of session, sonication delivery stamp, Active/Sham, transducer #, device operator, and all medical staff present during sessions. Only [name] will have access to this form to maintain the blind for *all* participants (e.g., another trained study team member may be unblinded to the treatment conditions for the particular subject(s) they are administering PLIFUS/sham for, but will not have access to the treatment conditions for other subjects).

6.1.11 Device Specific Considerations

See DEVICE MANUAL

6.2 *Study Behavioral or Social Intervention(s)*

6.2.1 Procedures for Training Interventionalists and Monitoring Intervention Fidelity

The training log for this study can be found in the regulatory binder.

An expert with extensive experience will be administering PLIFUS/sham. In the event that expert is unavailable to perform a subject's intervention visits, another trained study team member will administer PLIFUS/sham in his absence. In order to do so, this individual must be trained by the study's technical expert ([name]) and have both the DSMB's and technical expert's approval prior to PLIFUS/sham administration. Documentation of these approvals will be maintained in the regulatory binder in addition to the study training log. Of note, the same PLIFUS/sham administration will perform Intervention Visit 1 and 2 to maintain consistency. Those who administer PLIFUS/sham will be unable to rate outcome measures (AHRS, DESA, BPRS, and PSYRATS) for that subject.

Trained research assistants can administer the following scales: MoCA, CGI, BPRS, BPAQ, SAFTEE & addendum, AHRS, DESA, PSYRATS, and EHI. New research assistants will be trained before they may rate participants.

Only study team clinicians can complete the following assessments: Assessment of Capacity, SCID, and C-SSRS. Of note, study team clinicians can also administer any of the research assistant designated scales mentioned above.

7 Study Procedures and Schedule

7.1 *Study Procedures/Evaluations*

7.1.1 Study Specific Procedures

Assessments:

*Brief Psychiatric Rating Scale (BPRS)*⁴⁹: The BPRS is an 24-item scale that measures positive symptoms, negative symptoms, general psychopathology and affective symptoms. Individual items are scored on a seven point Likert scale. The BPRS has been extensively used in trials of antipsychotic agents and has been shown to be sensitive to change. Psychometric properties and the underlying factor structure are well-established. We will use a 1 week (7 day) lookback period for this clinical assessment.

*Buss-Perry Aggression Questionnaire (BPAQ)*⁴⁸:

The Buss-Perry Aggression Questionnaire consists of 29 items and contains 4 subscales: Physical Aggression, Verbal Aggression, Anger, and Hostility. The BPAQ will be administered at screening to assess a history of violence.

Structured Clinical Interview for the DSM-5 (SCID): The SCID for the DSM-V (Modules A-E) will be used to assess the primary psychiatric diagnosis for patients. The other modules for the SCID will not be performed as they do not relate to the inclusion/exclusion criteria.

Edinburgh Handedness Inventory (EHI)⁵⁰:

The EHI is a 10-item scale that measures laterality preferences when performing different tasks. Participants are asked to indicate which hand (right or left) they use when performing different actions. A laterality quotient is determined by calculating the percentage of activities that are completed solely with the right hand. A laterality score of 100 would reflect complete right-handedness. A score of 60% or greater will be used as the cutoff for right-handedness. Handedness will be recorded but is not an entry criterion.

Systematic Assessment for Treatment Emergent Side Effects (SAFTEE)⁵¹: The SAFTEE is a well-established and validated structured interview for assessment of side effects in intervention studies in schizophrenia. It consists of two components, an open-ended inquiry and a comprehensive review of all body systems.

An addendum to the SAFTEE will also be used to assess the following side effects that have been reported in other human subject ultrasound studies: mood deterioration, scalp heating, anxiety, neck pain, and pruritis (itching).

The Columbia Suicide Severity Rating Scale (C-SSRS)⁵²: The C-SSRS is a clinical interview that measures the spectrum of suicidal ideation and behavior. It was developed in the National Institute of Mental Health Treatment of Adolescent Suicide Attempters Study to assess severity and track suicidal events through any treatment. It can be administered during any evaluation or risk assessment to identify the level and type of suicidality present and can also be used during treatment to monitor clinical worsening. It contains a 1-to-5 rating scale for suicidal ideation of increasing severity. It contains a Screening scale and a Since Last Visit scale. This assessment will not be reported as unblinded in future publications.

Clinical Global Impression (CGI):

The CGI consists of three global scales (items) that have been designed to measure the severity of illness, global improvement, and efficacy of treatment. Global Improvement is the 2nd scale in the CGI. Total overall improvement is rated on a 0-7 point weighted scale, ranging from very much improved (1) to very much worse (7) respectively.

MRI:

A structural MRI will be performed using a PRISMA 3T scanner for the purpose of guiding neuronavigation of PLIFUS at the MRI Visit (approximately 10 minutes) and with each fMRI resting state scan (either before or after, approximately 5 minutes, to help register fMRI scans) on Intervention Visits 1 and 2. The structural MRI will be a standard clinical sequence. Three-D structural images will be acquired using a T1-weighted MPRAGE sequence (TR/TE = 2300 ms/2.96 ms, FOV= 256 × 256 mm², FOV phase=93.8%, acquisition matrix = 256 × 256, voxel size = 1 × 1 × 1 mm³, slice thickness = 1 mm, 192 sagittal slices).

fMRI:

Functional MRI will be performed before and after PLIFUS/Sham sessions to evaluate GPe functional connectivity. Data will be collected for 20 minutes using an echo-planar imaging sequence: repetition time/echo time (TR/TE) = 3000 ms/30 ms, field of view (FOV) = 216 × 216 mm², FOV phase = 100%, voxel size = 3 × 3 × 3 mm³, slice thickness = 3 mm, and 45 sagittal slices. Each functional run will contain 170 image volumes. All participants will be instructed to look at a fixation point on the screen and to not fall asleep during the resting-state data acquisition.

PLIFUS/Sham:

PLIFUS or sham will be performed in a procedure room adjacent to the MRI. Participants will be seated, gel will be applied to the right side of their head and the ultrasound transducer will be placed against the right side of their head. A water-filled membrane will occupy the space between the transducer and the participant's head. Sonication will be delivered in pulses over a 10 minute period. The sham procedure will be identical and will produce identical sounds so that neither the participant or the rater/psychiatrist will know which treatment modality is applied. Only the PLIFUS operator will be unblinded.

The Montreal Cognitive Assessment (MoCA):

MoCA is a widely used rapid screening instrument for mild cognitive dysfunction. It assesses different cognitive domains: attention and concentration, executive functions, memory, language, visuoconstructional skills, conceptual thinking, calculations, and orientation. It has little learning effect at one month and using alternative versions can decrease learning effect when used repeatedly^{53, 54}. For this study, we will use MoCA 8.1, 8.2, and 8.3.

*Psychotic Symptom Rating Scale (PSYRATS)*⁵⁵:

The PSYRATS is a well-validated 17 item, 5 point Likert scale which contains 6 items that characterize delusions according to 1.) Amount and duration of preoccupation, 2.) Conviction, 3.) Amount and intensity of distress, and 4.) Disruption to life. We selected the PSYRATS because it rates subjective distress and the degree to which delusions disrupt life. Factor analysis has revealed three dimensions: preoccupation, conviction and distress/life disruption, with modest correlation between preoccupation and conviction ($r=0.28$).

Auditory Hallucinations Rating Scale (AHRS):

A scale developed by Hoffman et al. measuring specific characteristics of auditory hallucinations (AHs) based on a 7-item scale⁵⁴. It is a reliable tool that has been used in multiple TMS studies to assess changes of AHs⁵⁶.

Delusions Experience Sampling Assessment (DESA):

Items regarding delusions from a validated experience sampling assessment^{57, 58} to assess moment-to-moment experience and detect more rapid changes of delusions. Participants will be asked to rate the same delusional belief at the moment on a 7-point Likert scale. It includes four items: conviction, distress, preoccupation, and disruption.

Communicating with Staff:

Study staff may use text messaging to communicate with subjects. This would only be for the coordination of study visits (i.e., if the subject is not available to do so over the phone and texting is easier at that moment), to ask the subject to give us a call back if they don't answer, or to confirm whether they are attending their study visit. Of note, the phone used by staff is an MCIT approved device, and phone number, as well as message history, will be deleted at subject's end of study/termination.

7.2 Study Schedule

7.2.1 Pre-Screening (Days -30 to -1)

- Review appropriateness for study with referring clinician
- Review medical and psychiatric history and current medications from the medical record (if available)

7.2.2 Screening Visit (Days -30 to -1)

- Complete quiz documenting the subject's understanding of study procedures, risks and alternatives.
- Complete Assessment of Capacity
- Obtain written informed consent.
- Complete Consent Checklist to document that informed consent procedures have been followed (i.e., Key Information Sheet provided, all questions were answered by study staff, consent given prior to any procedures being performed, etc.)
- Complete a medical and psychiatric evaluation by a study psychiatrist, including history and physical examination and recording of medications.
- Complete the Buss-Perry Violence Questionnaire by a research assistant
- Obtain urine sample for pregnancy test and urine toxic screen
- The psychiatrist will also complete a Structured Clinical Interview for DSM5 (SCID) to establish a diagnosis of schizophrenia or schizoaffective disorder and to assess exclusionary diagnoses, including substance use disorders
- The study psychiatrist will complete the Columbia Suicide Severity Rating Scale (C-SSRS), MoCA, and CGI.
- A research assistant will complete the Brief Psychiatric Rating Scale (BPRS) to determine whether the candidate meets symptom severity criteria.
- Determine eligibility based on inclusion/exclusion criteria

7.2.3 MRI Visit (Days -30 to -1)

- Obtain structural MRI scan for neuronavigation

7.2.4 Intervention Visits

Intervention Visit 1: (Day 0)

- Administer CGI, C-SSRS, SAFTEE, SAFTEE addendum, and PSYRATS
- Obtain structural MRI scan for fMRI registration (5 minutes)
- Obtain fMRI resting state scan (20 minutes)
- Administer AHRS and DESA prior to starting intervention
- Administer PLIFUS/sham over 10 minutes (re-administer AHRS and DESA at 5 minutes)
- Repeat AHRS and DESA immediately after PLIFUS/sham
- Obtain structural MRI scan for fMRI registration (5 minutes)
- Obtain fMRI resting state scan (20 minutes)
- AHRS and DESA repeated immediately after fMRI scan
- PSYRATS and CGI 60 minutes after PLIFUS/sham
- Psychiatric and medical assessment, including MoCA, SAFTEE, and SAFTEE addendum, 1 hour after PLIFUS/sham

Intervention Visit 1B: (Day 1-2) (may be remote)*

- AHRS and DESA
- SAFTEE & addendum
- C-SSRS

Intervention Visit 2 (Day 6-8)

- Administer CGI, C-SSRS, SAFTEE, SAFTEE addendum, and PSYRATS
- Obtain structural MRI scan for fMRI registration (5 minutes)
- Obtain fMRI resting state scan (20 minutes)
- Administer AHRS and DESA prior to starting intervention
- Administer PLIFUS/sham over 10 minutes (re-administer AHRS and DESA at 5 minutes)
- Repeat AHRS and DESA immediately after PLIFUS/sham
- Obtain structural MRI scan for fMRI registration (5 minutes)
- Obtain fMRI resting state scan (20 minutes)
- AHRS and DESA repeated immediately after fMRI scan
- PSYRATS and CGI 60 minutes after PLIFUS/sham
- Psychiatric and medical assessment, including MoCA, SAFTEE, and SAFTEE addendum, 1 hour after PLIFUS/sham

Intervention Visit 2B (Day 7-9) (may be remote)*:

- AHRS and DESA
- SAFTEE & addendum
- C-SSRS

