4.1 Description of Study Design

This is a single-site, phase 2, sham-controlled random-order cross-over pilot trial of PLIFUS targeting the right Gpi in individuals with schizophrenia. Twelve individuals with schizophrenia who report continuous hallucinations or delusions of moderate or greater severity will receive one session of PLIFUS and one session of sham PLIFUS in random order, one week apart. If no effect of PLIFUS is detected on measures of functional connectivity or psychotic symptoms in the first 12 completers with good quality imaging data, the trial will be changed to 3 sessions of PLIFUS or sham administered over 5 days for 4 subsequent participants.

Potential participants will be enrolled at NYU Langone Manhattan, NYU Langone Brooklyn, and Bellevue Hospital. Recruitment-only procedures will occur at Manhattan Psychiatric Center (see section 5.5.3). Following informed consent, potential participants will be screened by a psychiatrist who will assess psychiatric and medical status. A Brief Psychiatric Rating Scale will also be administered to assess inclusionary status. Individuals who meet inclusionary and exclusionary criteria will then have a structural MRI performed at the MRI visit and with each fMRI scan at Intervention Visits 1 and 2 to guide neuronavigation of PLIFUS. The two sessions of PLIFUS/Sham will occur in random order, one week apart. Randomization schedule will be done using Matlab. Participants will first have an fMRI for measurement of right Gpi functional connectivity, preceded and followed by symptom rating scales. PLIFUS/sham will then be administered over 10 minutes, during which symptom ratings will again be recorded. Symptom ratings will be repeated 5, 30, and 60 minutes, 1 day and 7 days post-sonication/sham. fMRI will be repeated starting 10 minutes after sonication/sham. Safety assessments will be completed prior to discharge of participants 1 hour after each sonication/sham session and after 24-48 hours and 7 days.

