addition to all adverse events recorded by the SAFTEE assessments, the DSMB will receive a report of any additional participant complaints, instances of participant distress, or breaches of confidentiality. Because this is a pilot study with a very small sample size, formal statistical criteria are not identified in advance for a stopping rule. The DSMB may halt the study for reasons of safety—we are not aware of any significant safety concerns. The DSMB must approve the decision to switch from one session of PLIFUS to 3 sessions if no effect is detected after the first 12 completers with good quality imaging data. A failure to detect an effect size of 0.5 or greater compared to sham on the AHRS, DESA, and PSYRATS total score or on GPi functional connectivity after the first 12 participants will define “no effect” and trigger a switch to 3 treatment sessions over 5 days for phase II of the study which will involve an additional 4 participants. The DSMB will also be provided copies of all communications with the IRB. The DSMB will meet prior to initiation of the study and a minimum of every six months and will be provided data regarding enrollment and side effects and a study summary prior to each meeting. [name] and study staff will not attend the closed section of the DSMB meetings. Throughout the study, notification of any Serious Adverse Events (SAEs) as well as any proposed investigator-initiated changes in the protocol will be submitted to the DSMB. Based on its review of the revised protocol, the DSMB will identify the data parameters and format of the information to be regularly reported. All SAEs and adverse events will be tabulated and submitted to the IRB and DSMB in the bi-annual (every 6 months) data reports or at the time of continuing review. AEs will be reported to the IRB annually (at continuing review) if they are expected, related, and harmful. A summary of the outcomes of the safety reviews as prepared for the DSMB along with accumulated adverse events and deviations will be submitted to the IRB as part of an annual progress report at the time of the Continuing Review submission.

8 Clinical Monitoring

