A study psychiatrist will be present during all sessions of PLIFUS and sham. Participants will be monitored during and after sonication until psychiatrically cleared by the study psychiatrist 1 hour after completion of each session. Participants will be contacted 24-48 hours and 7 days after each treatment period and symptoms, side effects and suicidality assessed.

9 Statistical Considerations

This is a pilot study intended to obtain preliminary data to guide future studies. The analysis will primarily be descriptive for this purpose and, due to the small sample size, effect sizes will be the primary signal of target engagement. Consistent with other studies in the field, we have selected an effect size of 0.5 as our threshold. In addition, there is a pre-planned review of results after completion of the first 5 participants; the administration of PLIFUS/sham will be increased from one session to three sessions over 5 days if an effect size of 0.5 or greater with PLIFUS is not detected in change from baseline in GPi functional connectivity or symptom response compared to sham.

The primary statistical analysis will be performed in completers without imputation of missing data and will be change in primary outcomes (GPi functional connectivity and symptom severity) from baseline to the first measure post-sonication or sham (immediately post-sonication for symptoms; 10-30 minutes for fMRI). PLIFUS and sham PLIFUS will be compared using a linear mixed effects model with baseline measures (GPI functional connectivity and severity of psychotic symptoms) as continuous variables; treatment (PLIFUS or sham) and sequence as categorical variables; and participant as a random effect. Similar secondary exploratory analyses will be performed at additional time points (symptom severity during sonication, 60 minutes, 1 day and 7 days after sonication). Secondary analyses of other outcome measures (BPRS total score, PSYRATS and CGI) will be analyzed following the same approach. Safety measures, including the SAFTEE and C-SSRS will be summarized descriptively. If the study design is adapted (sonication increased to 3 sessions) after the first 12 completers with good quality imaging data, results from the first 12 completers and subsequent 4 participants will be analyzed separately.

Sample Size

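### Section 9 plans a 60-minute symptom-severity analysis, but the visit lists schedule no AHRS or DESA at 60 minutes

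*Combined protocol and SAP*

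**What the plan says.** Section 9 sets the primary comparison as change from baseline to the first post-session measure, given as "immediately post-sonication for symptoms; 10-30 minutes for fMRI". It then adds: "Similar secondary exploratory analyses will be performed at additional time points (symptom severity during sonication, 60 minutes, 1 day and 7 days after sonication". PSYRATS is handled in a separate sentence: "Secondary analyses of other outcome measures (BPRS total score, PSYRATS and CGI) will be analyzed following the same approach".

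Section 4.1 promises, without naming a scale: "Symptom ratings will be repeated 5, 30, and 60 minutes, 1 day and 7 days post-sonication/sham". The Protocol Summary gives the same times.

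Section 7.2.4 is the list that staff will work from. At each intervention visit it places AHRS and DESA before the session, five minutes into it, directly after it, and directly after the post-session fMRI. The next AHRS and DESA are at the Day 1-2 contact (Visit 1B) or the Day 7-9 contact (Visit 2B). The one-hour entries are "PSYRATS and CGI 60 minutes after PLIFUS/sham" and a psychiatric and medical assessment for which MoCA, SAFTEE and its addendum are named. The Schedule of Events in Section 18 marks AHRS, DESA and PSYRATS at both interventions but gives no times within the visit.

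Section 7.15 defines a lack of effect, which triggers the move to three sessions, as follows: "A failure to detect an effect size of 0.5 or greater compared to sham on the AHRS, DESA, and PSYRATS total score". The imaging endpoint is the alternative measure in the same rule. No time point is named.

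**The concern.** The analysis section and the visit list disagree on what is rated one hour after the session. The visit list decides which data exist. A momentary rating that was not taken at 60 minutes cannot be recovered later: DESA asks about the belief as it is held at that moment.

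What is at stake is the description of how symptoms move after one session. With the lists as written, the AHRS/DESA course has no point between roughly half an hour and the next day. This is an exploratory result in a pilot, but a pilot of this kind exists to describe the time course for later trials.

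A smaller matter concerns the switch rule. It draws on three symptom scales whose first post-session values do not fall at the same time, and it does not say which value is used.

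**Working it through.** No power or sample-size figure bears on this point. The check sets the planned time points beside the scheduled ratings, with time zero at the end of the session.

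**Step 1. Which scale does symptom severity mean in Section 9?** The primary symptom measure is taken immediately after the session, and only AHRS and DESA are scheduled then. PSYRATS is placed among the other outcome measures. The natural reading is therefore AHRS and DESA.

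**Step 2. Planned time points against scheduled ratings (Sections 7.2.4 and 7.2.5).**

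| Section 9 time point | AHRS and DESA | PSYRATS |
|---|---|---|
| Baseline | yes, just before the session | yes, at the start of the visit |
| Immediately after (primary) | yes | no |
| During the session | yes, at 5 minutes | no |
| 60 minutes | **no** | yes |
| 1 day | yes (Visits 1B and 2B) | no |
| 7 days | yes (start of Visit 2; final visit) | after the first session only (start of Visit 2) |

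No scale covers the whole exploratory series. AHRS and DESA miss only the 60-minute point. PSYRATS has 60 minutes but lacks the during-session and 1-day points, and lacks 7 days after the second session.

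**Step 3. Can the post-fMRI rating stand in for 60 minutes?** The scan starts 10 minutes after the session (Section 4.1). The structural scan takes 5 minutes and the fMRI 20 (Section 7.2.4).

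- Structural scan first: 10 + 5 + 20 = 35 minutes.
- fMRI itself starting at 10 minutes: 10 + 20 = 30 minutes.

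The rating therefore falls about 25 to 30 minutes before the one-hour mark (60 − 35 = 25; 60 − 30 = 30). It fits the nominal 30-minute rating of Section 4.1, not the 60-minute one.

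**Step 4. Size of the gap.** 12 completers × 2 sessions = 24 sessions. Up to 24 AHRS values and up to 24 DESA values at 60 minutes would be missing. That is one of the four exploratory time points (during, 60 minutes, 1 day, 7 days).

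**Step 5. The switch rule.** PSYRATS has a pre-session and a 60-minute value in both periods, so a change score exists under PLIFUS and under sham for each completer, and an effect size can be computed. The intervals differ:

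- PSYRATS is rated before 5 + 20 = 25 minutes of scanning, so its change spans at least 25 + 10 + 60 = 95 minutes.
- AHRS and DESA, from just before to just after the session, span about 10 minutes.

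**The case against.** The strongest reply is that no section promises AHRS or DESA by name at 60 minutes. Section 4.2.2 lists PSYRATS among the clinical symptom endpoints, and PSYRATS is taken at 60 minutes, so a one-hour symptom rating does exist. The affected analysis is secondary and exploratory, and the Protocol Summary treats all results as exploratory. The primary symptom contrast is fully collected. This stands as far as it goes: it makes the point modest and leaves the sponsor a choice of remedy. It does not remove the mismatch, because Section 9 separates PSYRATS from symptom severity and PSYRATS cannot supply the rest of the series.

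Three stronger readings are tempting, and the documents do not support them.

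- A reader might infer that PSYRATS is not collected at all until 60 minutes, so that the switch rule cannot be evaluated. PSYRATS is given at the start of both intervention visits. The rule names no time point, and the Protocol Summary asks only for change from baseline to post-treatment. The rule is computable.
- A reader might infer that PSYRATS breaches the immediate time point of the primary analysis. Section 9 ties that time point to the primary outcomes and lists PSYRATS elsewhere. Its first post-session value is simply the 60-minute one.
- A reader might infer that the 30-minute rating in Section 4.1 is impossible because the participant is in the scanner. The post-fMRI rating at about 30 to 35 minutes is in effect that rating, and Section 9 plans no 30-minute analysis.

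**Conclusion.** The point holds in a limited form. The 60-minute symptom-severity analysis in Section 9 has no scheduled AHRS or DESA data, and the one-hour assessment lines and the Schedule of Events do not supply them. The loss is complete at that time point (up to 24 sessions) and nil for the primary contrast and for the other three exploratory time points.

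This rests on two assumptions: that symptom severity in Section 9 means AHRS and DESA, which its separate listing of PSYRATS supports, and that staff follow Section 7.2.4 as written. The count covers the 12 planned completers only. It is an upper limit because a participant may qualify on delusions without hallucinations, or the reverse.

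The switch rule needs its time points named, but this is a clarification. Nothing here shows that the rule fails or that a decision would change.

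**What to change.** Add AHRS and DESA to the 60-minute line of Intervention Visits 1 and 2 in Section 7.2.4. The participant is already present for PSYRATS, CGI, MoCA and SAFTEE, so the cost is a 7-item and a 4-item scale: a few minutes per session and one line of text per visit.

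If the sponsor meant PSYRATS to be the one-hour measure, then Section 9, Section 4.1 and the Protocol Summary should say so. That adds no rating, but the 60-minute result would then be on a different scale from the rest of the series.

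As a minor clarification, state in Section 7.15 which post-session time point feeds the 0.5 rule for each scale: for example, the immediate rating for AHRS and DESA and the 60-minute rating for PSYRATS. This costs one sentence and should be settled before the results of the first 12 completers are reviewed.
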